## **10. STUDY PROCEDURES**

### **10.1 Recruitment**

Our typical recruitment rates via GP practices is approximately one in ten people with T2DM. Recruitment via the local DESMOND course (T2DM education clinic) is approximately one in five people with T2DM. We will need to approach between 90 and 113 people with T2DM to ensure we recruit enough ( $n = 15$ ) people to account for drop outs.

Recruitment will be carried out by members of the UoP research team (or clinical team if participant clinical records are needed) acting with appropriate contracts with the responsible care organisation. The clinical staff will be briefed in detail regarding the current project and they will be provided with the inclusion and exclusion criteria of the study in order to perform any database searches. In the case of the computerised search of GP databases, this will be conducted by the direct healthcare team. Following receipt of the reply slips to the UoP research team, consent and screening will take place and results forwarded (for those willing) to our consultants who will review the results against the inclusion / exclusion criteria. Posters and word of mouth will also be utilised. Screening blood will be analysed at QA pathology or at a commercial pathology laboratory.

Inclusion criteria:

- Male or female (post-menopausal) aged 35 years or above.
- Diagnosed with T2DM as defined by the WHO ( $\geq 48$  mmol/mol).
- Participant is willing and able to give informed consent for participation in the study.
- Participant is able to understand and fully cooperate with the study protocol.

Exclusion criteria:

- Severe peripheral neuropathy (to the point to which they cannot sense temperature)
- Uncontrolled hypertension ( $\geq 180$  systolic / 100 diastolic mmHg)
- Taking any medication which may interfere with data interpretation or safety
- Who have had a myocardial infarction or cerebro-vascular event
- Any cardiac abnormalities which restrict hard exercise

- Current smokers or who have stopped within 3 months
- Participant is unable to understand and/or fully cooperate with the study protocol
- Any other serious medical condition which would interfere with data interpretation or safety will be excluded from participation.
- Skin ulcerations
- Eczema
- Pre-existing postural hypertension
- Existing cardiac diseases (identified during screening)

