## 2. SYNOPSIS

Study Title	The Effect of Chronic Passive Heating on Insulin Sensitivity and Cardiovascular function in People with Type 2 Diabetes Mellitus: A pre- and post-test trial.
Internal ref. no.	n/a
Problem statement	
Type 2 diabetes mellitus (T2DM) is a metabolic condition characterized by chronic hyperglycemia and progressive insulin resistance, which progressively lead to macro- and microvascular damage and subsequent impairments in blood pressure (BP) control. Therapeutic approaches to manage T2DM focus on improving glycaemic control and BP and include pharmaceutical treatments (e.g. Metformin and insulin), physical activity and exercise, and calorie restriction. However, pharmaceutical interventions can be expensive and are associated with low adherence. Although exercise and diet programs have been shown to be effective, like pharmaceutical interventions, they often have poor adherence in people with T2DM. With the number of people with T2DM (464 million) continuing to rise and expected to reach 700 million by 2045, the costs associated with the clinical management of this condition are likely to become unsustainable. There is, therefore, a need to explore the potential of alternative interventions. In particular, interventions which may be cheaper than clinical management and have better adherence than exercise, and hypoglycemic agents, to improve glycemic control and deleterious cardiovascular manifestations of this condition.

	Passive heating may be one such intervention with therapeutic potential.
Research question / hypothesis	
Before passive heating can be considered as a therapeutic option for improving metabolic and cardiovascular health in individuals with T2DM, we need to explore whether their chronic passive heating (1h x 10 days) is able to improve:
 
 
1) insulin sensitivity
 
2) glycaemic control
 
3) metabolic efficiency
 
4) vascular health
 

Study Design	We plan to run a within-subject, pre-, post-intervention study
Study Participants	Adults $\geq$ 35 years (post-menopausal for females), diagnosed with T2DM as defined by the world health organisation (WHO).
Planned Sample Size	We aim to recruit 20 individuals with T2DM.
Follow-up duration	7 days
Planned Study Period	18 months

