Primary Objective	To determine whether chronic passive, warm water therapy increased insulin sensitivity in individuals with T2DM?
Secondary Objectives	
To determine whether chronic passive, warm water therapy improves:
 
 
1) glycaemic control
 
2) metabolic efficiency
 
3) vascular health
 

Primary Endpoint	Improvement in insulin sensitivity from chronic passive heating.
Secondary Endpoints	

1) fasting plasma [glucose]

2) AUC plasma [glucose]

3) peak plasma [glucose]

4) HbA1c

5) plasma [eHSP70]

6) plasma [IL-6]

7) plasma [IL-10]

8) plasma [butyrate]

9) plasma [growth hormone]

10) RMR

11) fat oxidation

12) CHO oxidation

13) macrovascular function

14) microvascular function

15) resting heart rate

16) stroke volume

17) total peripheral resistance

	18) cardiac output  19) heart rate variability
Intervention (s)	8-12 x1 h water immersion (to the clavicle, @40 °C, rectal temperature ~38.5 °C and <39 °C) sessions over a period of 14 days.

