#### 4. BACKGROUND AND RATIONALE

Current estimates suggest 422 million people worldwide live with a form of diabetes, of which ~ 90% have type 2 diabetes mellitus (T2DM) [1]. The total direct and indirect cost of care for individuals with diabetes in the UK is £23.7 billion, equating to ~ 20% of the annual NHS budget [2], this figure is expected to rise to ~£39.8 billion by the year 2035 [2, 3]. Approximately 85-90% of cases of T2DM arise from a poor lifestyle and obesity [4-6], with the remaining 10-15% resulting from genetic predispositions [7, 8]. Current interventions include pharmaceutical treatments, exercise and calorie restrictive diets, which aim to improve glycaemic control. However, pharmaceutical interventions carry a high financial cost [9, 10], while exercise and diet programmes have a low adherence rate in individuals with T2DM [10-15]. With the prevalence of T2DM continuing to increase, the costs associated with the clinical care of these individuals are likely to become unsustainable. Simple, inexpensive interventions to improve the clinical profile of this group are therefore needed.

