## 9. SAMPLING

An *a priori* sample size calculation was performed based on a passive heating study assessing insulin sensitivity in health individuals [60]. The mean difference between pre and post chronic passive heating was  $16 \pm 14.5$  a.u. for insulin sensitivity ( $\sim 1\text{SD}$ ). For 80% power and an  $\alpha$ -

level set at  $P = 0.05$  (two tailed), to detect a 1 SD difference 15 individuals are required. In order to account for dropout, we anticipated that 20 individuals would need to begin the study.

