#### 10.2 Participants approach strategy

The clinical team will provide interested parties with an invitation letter and the PIS when they attend the clinic. Additionally, the clinical team may send out an invitation letter including a return slip to potential participants on their clinic list or GP database, who could then opt in to finding out about the study. A member of the UoP research team will attend the DESMOND meeting 3 times a month to advertise, discuss and disperse information about the study.

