#### 10.4 Randomisation

Due to study design, randomisation will not be necessary.

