### 11.4 Concomitant Medication / Therapies

Medication will be recorded on enrolment and updated throughout their time on the trial. For each experimental visit, hypoglycaemic aids will be stopped for the morning (see pre experimental instructions for details).

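### Single-arm pre-post trial recruits partly at a diabetes education course and does not bar recent or ongoing changes in therapy or lifestyle, so drift of unknown size and direction enters the primary change

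*Combined protocol and SAP*

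**What the plan says.** The synopsis describes the design: "We plan to run a within-subject, pre-, post-intervention study". Section 10.4 adds: "Due to study design, randomisation will not be necessary". The synopsis gives the primary endpoint as "Improvement in insulin sensitivity from chronic passive heating". Section 7.2 names the outcome simply as insulin sensitivity, and section 10.6 calculates it by the Gutt method.

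Sections 7.1 and 10.1 list hospital outpatients, GP practices, posters and word of mouth as recruitment sources. Section 10.1 also gives yields: about one in ten through GPs, and for the course, "Recruitment via the local DESMOND course (T2DM education clinic) is approximately one in five people with T2DM". Under section 10.2 a member of the research team "will attend the DESMOND meeting 3 times a month to advertise" the study.

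The criteria in 10.1 contain no stable-therapy requirement, no interval after the course and no minimum time since diagnosis. The only look-back window is three months for stopping smoking. One exclusion covers drugs that could interfere with interpretation or safety, without defining them. Section 11.4 says: "Medication will be recorded on enrolment and updated throughout their time on the trial".

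Section 14.1 analyses everyone with both experimental visits and at least 8 immersions. Section 14.2 specifies an unadjusted paired t-test or Wilcoxon signed-rank test. Sections 14.1 to 14.3 do not mention the medication record or the food and activity log.

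**The concern.** In a single-arm pre-post study, everything that changes between the two visits is part of the estimate. The background section of the protocol lists other influences on glycaemic control: "Current interventions include pharmaceutical treatments, exercise and calorie restrictive diets, which aim to improve glycaemic control". People met at an education course may be starting to act on what they learn there, and people from any route may have had their treatment altered recently or may have it altered during the 14-day block. Nothing in the criteria keeps such people out, and nothing in the analysis shows how much they contribute.

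At stake is the meaning of a positive result. The test asks whether the mean change differs from zero, while the synopsis endpoint reads that change as the effect of heating. A larger sample does not help, because it makes a given drift more likely to reach significance.

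**Working it through.** **Inputs from the documents.** Two-sided alpha 0.05, paired comparison, 15 evaluable and 20 recruited (7.1, 9). Source-study change 16 ± 14.5 a.u. (9). Immersions within 14 days (10.5). Visits less than 72 h before and after the intervention (10.6).

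**Assumption.** The documents give no figure for drift, so a range is used, in SDs of the individual change. On the source study's scale 0.1 SD is 0.1 × 14.5 = 1.45 a.u. That study was in healthy people, so the conversion is only indicative.

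**1. The plan's own figure.** Section 9 says "two tailed), to detect a 1 SD difference 15 individuals are required". For a paired t-test, power is the probability that a noncentral t with n − 1 degrees of freedom and noncentrality d√n falls beyond ±t(0.975, n − 1). At d = 1 this gives 80.3% at n = 10 and 94.9% at n = 15. The stated 15 is therefore not reproduced for 80% power. The mismatch errs towards more people and does not bear on this point.

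**2. Time available for drift.** 3 + 14 + 3 = about 20 days at most.

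**3. Uniform drift, no heating effect.** If everyone drifts by d SD in the favourable direction, the chance of a significant improvement is P[T(n − 1, d√n) > t(0.975, n − 1)], with critical values 2.093 (n = 20) and 2.145 (n = 15).

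| d | n = 15 | n = 20 |
|---|---|---|
| 0 | 2.5% | 2.5% |
| 0.05 | 3.8% | 4.0% |
| 0.1 | 5.5% | 6.2% |
| 0.2 | 10.8% | 13.3% |
| 0.3 | 19.0% | 24.6% |

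**4. Drift in a subgroup, no heating effect.** Suppose k of n people shift by 1 SD and the rest do not. The mean shift is k/n: 4/20 = 0.2 SD and 6/20 = 0.3 SD. The spread also grows, with expected sample variance 1 + (k/n)(1 − k/n) × n/(n − 1). The SD becomes √(1 + 0.2 × 0.8 × 20/19) = 1.08 for k = 4 and √(1 + 0.3 × 0.7 × 20/19) = 1.11 for k = 6. Simulating 400,000 trials with normal changes gives 10.4% for 4 of 20 and 18.7% for 6 of 20. With 15 evaluable, 3 of 15 gives 8.2% and 5 of 15 gives 16.8%.

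**5. What the existing controls cover.**

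| Control | Covers | Leaves open |
|---|---|---|
| 12 h fast, 48 h without exercise, 24 h without alcohol and caffeine, diabetes drugs omitted on the test morning (7.1) | Acute effects on the test day | Changes in regimen, diet or activity over the preceding weeks |
| 48 h food and activity log (10.6) | Records the two days before a visit | Not used in the analysis |
| Exclusion of interfering medication (10.1) | Taking a drug | Starting, stopping or changing one; lifestyle |
| Medication record (11.4) | Captures changes | Not used in the analysis |

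The medication exclusion cannot mean all glucose-lowering drugs, since 7.1, 11.4 and 15 have participants omit theirs only on the test morning.

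**The case against.** Four counter-arguments have weight.

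- **The design is declared.** The title calls this a pre- and post-test trial, section 6 speaks only of potential as a future treatment, and 7.2 words the outcome neutrally. This stands: the causal endpoint wording is one synopsis line, and correcting it is largely editorial. But where there is no comparator, eligibility and sensitivity analysis are the main protections left, and neither deals with drift.
- **The plan has safeguards.** The test-day restrictions and short gap do limit drift, and consultants reviewing screening results could use the medication exclusion to turn away someone who has just started a drug. That discretion is undefined and does not reach lifestyle change.
- **The illustration is generous.** One SD is about the whole effect the trial is sized on, and nothing in the documents shows that a fifth or more of participants would gain it from other causes in under three weeks. This stands, which is why the small-drift rows matter.
- **The remedies are partial.** Excluding people on a post-baseline event is imperfect in a sample of 15 to 20, and it does not touch lifestyle drift. This also stands.

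A reader might go further than the documents allow in four ways.

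- *That the trial seeks or expects people with changing medication.* It only fails to bar them, and updating a medication record is ordinary practice.
- *That most participants come from the course.* One in five is a yield per person approached. The share recruited there, the course content and the time from course to pre visit are not given.
- *That drift must favour heating.* A dose reduction, for instance, could push the other way.
- *That the false-positive rate is 13-25%.* That applies the 0.2-0.3 SD average to everyone and ignores the extra spread when only some people shift.

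**Conclusion.** The point holds as a gap in protection against bias. The plan does not bar recent or ongoing changes in glucose-lowering therapy or lifestyle programmes, has a single pre visit, and leaves the records it collects out of the analysis. Any such change enters the primary difference and, on the synopsis wording, is credited to heating.

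The size is unknown. Under the assumed ranges at n = 20 with no heating effect, the chance of a significant improvement is about 4-6% for a uniform favourable drift of 0.05-0.1 SD and about 10-19% if 4-6 of 20 people shift by 1 SD, against 2.5%. These figures rest on normally distributed changes, favourable drift and the assumed sizes. They show sensitivity and do not predict what will happen. The change is worth making because it is cheap; the documents do not show that the result will be wrong.

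**What to change.** 1. **Section 10.1.** Add a criterion that glucose-lowering therapy has been unchanged, and any structured education or lifestyle programme completed, for an interval before the pre visit that the sponsor defines. This governs eligibility and timing only. People met at the course can be consented there and have their pre visit scheduled later. Cost: some delay within the February to October 2021 recruitment period (section 18) and a few ineligible candidates.
2. **Section 14.2.** Alongside the main analysis, repeat the primary comparison without participants whose recorded glucose-lowering medication changed between the visits, and report how many there were. Cost: one extra run on data that 11.4 already collects. State that it does not address lifestyle drift.
3. **Synopsis.** Align the primary endpoint with 7.2 and 10.6 as the change in the Gutt index from the pre to the post visit, and state that attribution to heating needs a controlled comparison. Cost: wording only.

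These steps reduce the opportunity for drift and make part of it visible. They do not replace a comparator.

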#### 10.2 Participants approach strategy

The clinical team will provide interested parties with an invitation letter and the PIS when they attend the clinic. Additionally, the clinical team may send out an invitation letter including a return slip to potential participants on their clinic list or GP database, who could then opt in to finding out about the study. A member of the UoP research team will attend the DESMOND meeting 3 times a month to advertise, discuss and disperse information about the study.

#### 10.3 Screening and Enrolment

**Consent and Screening:** Visit 1 will act as a screening, consent and baseline assessment (~1 h). Participants will be given the opportunity to ask any questions they may have after reading the PIS. A standard medical history and clinical examination will be undertaken by a member of UoP staff, including height, mass, electrocardiogram, full blood count and HbA1c. Seated resting blood pressure measurements will be performed to calculate systolic, diastolic blood pressure.

#### 10.4 Randomisation

Due to study design, randomisation will not be necessary.

#### 10.5 Study intervention

*Daily passive heating:* Participants will attend the laboratory on 8-12 occasions within a period of 14 days (~ 90 min per visit) with the aim of completing 10, at any point in the day. Anyone completing less than 8 will be excluded from analysis. During each visit participants will self-insert a rectal thermistor and will then be immersed into a hot tub (~ 40 °C) for 60 min. Body position will be manipulated as required to achieve and maintain a target  $T_{rec}$  at 38.5 °C using 40 °C water. Aural temperature will also be measured every 15 min for determination of

validity and time lag compared to  $T_{rec}$ , for possible use in future studies. BP will also be measured at 15 min intervals after passive heating in the first intervention visit to firstly, establish safety data on the protocol (i.e. to avoid syncope) and secondly, be used as a benchmark for recovery time in subsequent intervention visits. Participants will be required to wear a bathing suit and a t-shirt for all heating visits.

## 10.6 Study Assessments

Study assessments of the outcome measures will take place before ( $< 72$  h) and after ( $< 72$  h) the intervention. The pre- and post- experimental visits should take  $\sim 3$  hours. Briefly, in line with OGTT guidelines, participants will arrive at  $\sim 0800$  following an overnight fast. The research coordinator will confirm with the participants that they have completed a 48 h food and physical activity log, that no exercise has been performed and that no alcohol or caffeine has been consumed on the day before. To ensure that participants arrive in a euhydrated state, they will be asked to consume  $\geq 17$  mL·kg $^{-1}$  of water before each visit. Participants will rest for 15 min in a semi-recumbent position, in comfortable ambient conditions (23 °C, 50% relative humidity), then have baseline bloods (collected via venipuncture), ECG, central haemodynamics, RMR collected / measured and brachial artery FMD measurements will start followed by iontophoresis. At  $\sim 0830$  a 2 h OGTT will start with the ingestion of a glucose drink (Rapilose, 75 g glucose). At the end of the OGTT after bloods have been taken again, participants will be provided with a snack. A detailed description of the outcome measures are given below.

### **Primary Outcome:**

*Insulin sensitivity:* Venous blood will be drawn in a fasted state after a resting period of 15 min for analysis of plasma [glucose] (Fluoride/Oxalate tubes, BD, USA) and [insulin] (EDTA tubes, BD, USA). An OGTT (75 g glucose solution) (Rapilose OGTT solution, Penlan healthcare, Japan) will then start and after 120 min of rest, venous blood will be drawn again. Insulin sensitivity will then be calculated via the Gutt method [61].

### **Secondary Outcomes:**

#### *Biomarkers*

Blood samples will be taken at screening in EDTA tubes for assessment of full blood count and HbA1c. Fasting and area under the curve (AUC) plasma [glucose] will be assessed as a marker of glucose control. Change in circulating plasma [Growth Hormone (GH)] (EDTA, K2, BD, NJ, USA) will be assessed due to its diabetogenic effects via gluconeogenesis and glycogenolysis from the liver and kidneys and suppression of glucose uptake in adipose tissue [59, 60]. Change in circulating plasma [Butyrate] (EDTA K2, BD, NJ, USA) caused from alterations in gut microbiome [64] will be assessed due to its effect on insulin secretion [65],

insulin action [65] and inflammatory status [66]. Change in circulating plasma [eHSP70] (EDTA K2, BD, NJ, USA) will be assessed due to eHSP's role in reducing inflammatory status. Change in circulating plasma [IL-6] (EDTA K2, BD, NJ, USA) and [IL-10] (LH, BD, NJ, USA) will be assessed to determine inflammatory status. Blood samples for assessment of fasting plasma [glucose], HbA1c, [GH], [Butyrate], [eHSP70], [IL-6] and [IL-10] will be from the venous collection at a fasted state and at the end of the 120 min OGTT for AUC plasma [glucose] and insulin sensitivity only. With exception to screening samples which will be taken for analysis immediately after visit, all samples will be immediately placed in a chilled (4°C) centrifuge and spun at 4000g for 10 min. Once spun, the plasma will be pipetted into Eppendorf's and placed into a -80°C freezer for storage. Additional biomarkers may be looked at in future if extra funds become available.

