## 7. STUDY DESIGN

### 7.1 Summary of study design

**Plan of investigation:** We plan to run a pre-, post-intervention study to assess chronic heating's effect on metabolic health and cardiovascular function in people with T2DM. We aim to recruit 20 individuals with T2DM. All visits (11-15) will take place within our physiology laboratories (Spinnaker Building, University of Portsmouth). The experimental design will involve an initial screening visit (~1 h), two identical experimental visits (pre and post intervention) (~3 h) and 8-12 intervention visits (~1.5 h) (see Figure 1). We will aim for 10 intervention visits [57], however for feasibility we have incorporated scope for plus or minus 2 immersions for individuals who want to come for extra visits or struggle with time constraints. Both longer [58] and shorter protocols [59] have been utilized in the past. The screening visit will consist of participant characterisation, safety assessments including resting electrocardiogram (ECG), screening bloods (HbA1c, FBC, liver and renal function) and familiarisation with the testing procedures. On experimental visits, the participants will arrive at 0800 in a fasted state (12 h), and will have refrained from exercise 48 h before, alcohol and caffeine 24 h before, and taking any diabetes medication the morning of the visit. Participants will then undergo: baseline measurements of bloods, central haemodynamics, RMR, macro- and microvascular function; then an oral glucose tolerance test (OGTT) and re-measurements of blood (for analysis of plasma [glucose] and [insulin] only here). After the OGTT participants will be provided with a snack.

The intervention visits consist of the participant being immersed into a 40 °C hot tub for 1 h with rectal temperature measured throughout to ensure target deep body temperature is attained (38.5 - 39°C) and to also monitor deep body temperature for safety (see 10.5). To clamp deep body temperature, body position in the hot tub will be manipulated accordingly to allow heat loss to occur. If rectal temperature goes above 39 °C the heating protocol will be terminated and cool procedure enacted. Visit measurements and time course are explained in detail in section 10.6.

[figure not shown]

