## 7.2 Primary and Secondary Endpoints/Outcome Measures

The primary outcome of this study is insulin sensitivity. Secondary outcomes are:

- 1) fasting plasma [glucose]
- 2) AUC plasma [glucose]
- 3) peak plasma [glucose]
- 4) HbA1c
- 5) plasma [eHSP70]
- 6) plasma [IL-6]
- 7) plasma [IL-10]
- 8) plasma [butyrate]
- 9) plasma [growth hormone]
- 10) RMR
- 11) fat oxidation
- 12) CHO oxidation
- 13) macrovascular function
- 14) microvascular function
- 15) resting heart rate
- 16) stroke volume
- 17) total peripheral resistance
- 18) cardiac output
- 19) heart rate variability

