## **15. ETHICS**

NHS Local Research Ethics Committee (REC) approval will be obtained prior to commencement of the study. The REC, local NHS, research and development department and all site specific forms and participant identification centre forms will be forwarded to the R&D department at Queen Alexandra Hospital Portsmouth, prior to recruitment of participants. Written informed consent will be obtained from all participants. Insurance indemnity will be provided by the University of Portsmouth for this study.

Every effort has been made to keep the risks and discomforts to a minimum, with first aid cover and extensive screening procedures in place but there are some risks associated to taking part.

Not all volunteers will experience any or all of the risks stated below, but participants will be made aware of them.

The main burden to participants is a 12 h fasting period before their experimental visits. Participants will be asked to cease all hypoglycaemic agents on the morning of testing and will be instructed to bring them with them on the day. This is in line with a normal fasted OGTT typically used in clinics. Prior to leaving the laboratory, participants will be provided with lunch, they can take their tablets and blood sugars checked prior to leaving.

We will also be asking people with T2DM to be immersed in 40 °C water for all intervention visits. This may cause some discomfort which will be assessed with a thermal sensation and comfort scale. We will be measuring the core temperature via rectal thermistor and monitoring it closely at all times. Participants will be reminded that they are free to withdraw at any time point and will also be withdrawn and cooled if  $T_{rec}$  raises above 39°C (as stated in the school SAP's).

Participants will be asked to insert a rectal thermistor on 8-12 occasions (water immersions). This can be uncomfortable upon insertion; however, this is necessary for safety purposes. Participants will be provided with lubrication and instructions.

Other less burdensome tests will be performed such as:

Blood pressure; participants will feel a cuff squeeze their arm and this can be uncomfortable for a few moments. Blood samples taken via intravenous access can cause discomfort associated with insertion of the needle.

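### AUC and peak plasma glucose are undefined secondary endpoints, and the two OGTT draws described (fasting and 120 min) cannot measure either.

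*Combined protocol and SAP*

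**What the plan says.** AUC and peak plasma glucose are items 2 and 3 of the 19 secondary endpoints, both in the synopsis ("2) AUC plasma [glucose]") and in section 7.2 ("3) peak plasma [glucose]"). The value at 120 min is not itself a listed endpoint.

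On sampling, the primary-outcome text in section 10.6 describes a fasting venous draw and then says that the OGTT "will then start and after 120 min of rest, venous blood will be drawn again". The biomarker text assigns the second sample: "at the end of the 120 min OGTT for AUC plasma [glucose] and insulin sensitivity only". The visit narrative in the same section agrees ("At the end of the OGTT after bloods have been taken again"), and so does the legend to Figure 1.

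Two places are looser. Section 7.1 speaks of "re-measurements of blood (for analysis of plasma [glucose] and [insulin] only here", with no number or times. Section 15 says "Blood samples taken via intravenous access can cause discomfort associated with insertion of the needle", which names no extra draw.

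On definition, the only text about AUC glucose is "Fasting and area under the curve (AUC) plasma [glucose] will be assessed as a marker of glucose control". That gives a purpose but no calculation. Peak glucose is not mentioned outside the two endpoint lists. Section 14.2 names the paired tests but gives no derivations, and section 14.4 says that no further analysis plan is required.

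**The concern.** An AUC and a peak are meant to summarise how glucose rises and falls after the load. With one value before the load and one at 120 min, nothing is observed in between. Three consequences follow if sampling is as described.

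- A treatment effect confined to the interval between the draws leaves both endpoints unchanged.
- A change in 2-h glucose alone moves AUC and, when G120 exceeds G0, peak as well. One measurement then appears as two results in the paired tests.
- Because total or incremental AUC is not specified, a change in fasting glucose alone moves AUC in opposite directions under the two readings, and the choice could be made after the data are seen.

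Glycaemic control is the first of the three secondary objectives. Readers would take results labelled AUC and peak as evidence about the glucose excursion, which the described data cannot supply.

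**Working it through.** The plan gives no figure for these endpoints, so there is nothing to reproduce. The check asks what the described draws can yield.

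**Inputs.** From section 10.6: draws at 0 min (G0) and 120 min (G120). Assumed for comparison only: a five-point grid (0/30/60/90/120 min) and a three-point grid (0/60/120 min). Neither grid is in the documents.

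**Formulas (trapezoid).**
- Two-point total AUC = 120 × (G0 + G120)/2 = 60 × (G0 + G120).
- Two-point incremental AUC = total − 120 × G0 = 60 × (G120 − G0).
- Two-point peak = max(G0, G120).
- Weights in minutes: five-point 15, 30, 30, 30, 15; three-point 30, 60, 30; two-point 60, 60.

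**Pre-to-post change in AUC (mmol/L·min).**

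| Change in glucose | Five-point | Three-point | Two-point | Two-draw peak (mmol/L) |
|---|---|---|---|---|
| (1) −2 mmol/L at 30, 60 and 90 min | 3 × 30 × (−2) = −180 | 60 × (−2) = −120 | 0 | 0 |
| (2) −1 mmol/L at 120 min only | −15 | −30 | −60 | −1.0 if G120 stays above G0 |
| (3) −1 mmol/L at 0 min only, total AUC | −15 | −30 | −60 | 0 if G120 > G0 |
| (3) the same, incremental AUC | −15 + 120 = +105 | −30 + 120 = +90 | −60 + 120 = +60 | 0 if G120 > G0 |

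Rows (1) and (2) are the same for total and incremental AUC because G0 does not change. For an incremental area that counts only values above fasting, this also requires all values to stay above fasting. In row (2) the two-point change is 60/15 = 4 times the five-point change and 60/30 = 2 times the three-point change.

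**Can two draws tell curves apart?** Three assumed profiles share G0 = 8 and G120 = 13 mmol/L:

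| Profile at 0/30/60/90/120 min | Five-point total AUC | Five-point incremental AUC | Five-point peak |
|---|---|---|---|
| 8, 11, 13, 13.5, 13 | 1440 | 480 | 13.5 |
| 8, 13, 16, 15.5, 13 | 1650 | 690 | 16 |
| 8, 14, 18, 17, 13 | 1785 | 825 | 18 |

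With two draws all three give total AUC 60 × 21 = 1260, incremental AUC 60 × 5 = 300 and peak 13. The two-point total is 1260/1785 = 71% to 1260/1440 = 88% of the five-point value. The two-point peak is 0.5 to 5 mmol/L too low.

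**The case against.** The strongest reply is that the text may under-describe the sampling. The image of Figure 1 is not available, section 7.1 uses an untimed plural, and section 15 mentions intravenous access. This stands as a limit: the documents do not prove that intermediate samples are absent. But every draw that has a time is fasting or 120 min, and section 10.6 says that the baseline bloods are taken by venipuncture. If further draws exist, their times and both definitions are still missing.

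A second reply is that a two-point AUC can be computed, and that labelling it as such and naming total or incremental would disturb the plan less. It can be computed, but it is a fixed combination of G0 and G120. Fasting glucose is already endpoint 1, so beside 2-h glucose such an AUC adds nothing.

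Third, AUC has a stated purpose and an assigned sample. That is true, but neither is a definition.

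Fourth, the scenarios are limiting cases on assumed grids, and AUC and peak rest on exactly the same measurement only when 2-h glucose alone changes. This also stands. The figures show what the endpoints can miss or distort, not how much they will in this trial.

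**Conclusion.** The concern holds. Followed as written, the plan would report two secondary endpoints that do not measure what their names say. AUC reduces to a sum or difference of fasting and 2-h glucose, and its direction can depend on an unstated choice. Peak reduces to the larger of the two values, which is the 2-h value whenever G120 exceeds G0.

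The size in the illustrations is −180 against 0 mmol/L·min for a change between the draws, a four-fold overweighting of a change at 120 min relative to five points, and −60 against +60 for a change in fasting glucose alone. The arithmetic is exact given the trapezoid rule and the assumed grids; how likely each pattern is cannot be derived from the documents.

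The reach is 2 of 19 secondary endpoints. The primary insulin sensitivity index, fasting glucose and HbA1c are not affected by this point. It should be fixed, but it does not threaten the primary analysis.

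**What to change.** Issue a dated amendment that gives the number of participants already tested and first states which OGTT draws are actually taken.

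**If only the fasting and 120-min draws are taken:**
- In the synopsis and section 7.2, replace the AUC and peak entries with one endpoint: 2-h plasma glucose, from the venous sample at 120 min of the OGTT.
- In section 10.6, change AUC to 2-h plasma glucose in both biomarker sentences: the one on markers of glucose control and the one that assigns the end-of-OGTT sample.
- Make no claim about AUC or peak.

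**Only if intermediate samples are in fact already being drawn:** keep both endpoints and write into section 10.6 the draw times, the AUC formula (trapezoid, with either total or incremental named) and the definition of peak as the highest of the listed draws.

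**Cost.** Neither branch needs new samples. The first leaves one secondary endpoint fewer and no statement about glucose between 0 and 120 min. It also changes pre-specified endpoints after the scheduled start of data collection (March 2021, section 18) and must be reported as such; the dated amendment makes that visible but does not remove it. The second branch costs text only.
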